**Optimizing the Effectiveness of Routine Post-Treatment Surveillance
in Prostate Cancer Survivors**

National Clinical Trial (NCT) Identification Number: NCT02957357

Principal Investigator: [name]

20 Dec 2016

Study Protocol and Statistical Analysis Plan

Specific Aim 1: Compare patient-centered outcomes (including survival, procedures/tests, treatments) in prostate cancer survivors followed with alternative surveillance frequencies.

Hypothesis: More frequent surveillance increases the receipt of additional procedures and tests in all groups of patients, but improves survival only in patients with high-risk prostate cancer.

Synopsis: We will analyze data from the National Cancer Data Base (NCDB), which includes real-world prostate cancer treatment, surveillance and outcomes data on ~70% of US patients. We will compare the effectiveness of the three most common surveillance frequencies (PSA testing every 3 months vs. 6 months vs. 12 months) stratified by risk of recurrence and initial treatment (surgery or radiation).

Introduction: The primary goal for PSA surveillance after prostate cancer treatment is to detect recurrent cancer, thus allowing provision of additional treatments which can improve survival.^{1,2} Intuitively, patients who are most likely to recur after initial treatment (“high risk” cancer) may require more frequent surveillance, while those least likely to recur (“low risk”) may require less frequent surveillance. Further, patients treated by surgery vs. radiation may require different surveillance frequencies because the definitions of recurrence differs by treatment, and false positives from surveillance PSA are much more common after radiation.^{3,4} These considerations underlie the rationale to examine outcomes separately in 6 individual groups based on *standard definitions* of recurrence risk⁵ and initial treatment:

- Low-risk prostate cancer (defined by clinical stage \leq T2a, PSA <10, and Gleason score \leq 6): Recurrence risk is <10%.⁶ Two cohorts will be examined separately, 1) those treated with **initial prostatectomy**, and 2) those treated with **initial radiation** (including external radiation and/or brachytherapy).
- Intermediate-risk prostate cancer (defined by clinical stage T2b-c, and/or PSA 10-20, and/or Gleason 7): Recurrence risk is ~30%.⁷ Two cohorts will be examined separately, 3) those treated with **initial prostatectomy**, and 4) those treated with **initial radiation**.

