- High-risk prostate cancer (defined by clinical stage \geq T3, PSA >20, or Gleason 8-10): most aggressive type of prostate cancer. Recurrence risk is ~50%.⁷ Two cohorts will be examined separately, 5) those treated with **initial prostatectomy**, and 6) those treated with **initial radiation**.

[figure not shown]
The objective of this aim is to quantify the potential benefits (survival) and harms (procedures/tests, treatments) of different PSA surveillance frequencies in the 6 patient groups, which are currently unknown. It is intuitive that more frequent surveillance will lead to more findings of elevated PSA, thus leading to more downstream procedures and tests, and treatments; with unclear survival benefit. The *rationale* for this aim is that successful completion of the proposed research will contribute novel, currently unavailable, data to inform patient decision-making.

Comparators [RQ-5]: We selected our comparators of surveillance frequency based on published recommendations and by engaging diverse stakeholders (including clinicians who specialize in prostate cancer care). The three most common surveillance frequencies in clinical

practice are every 3, 6, or 12 months. In each of the 6 patient groups, patient outcomes of every 3 vs. 6 vs. 12 month surveillance will be directly compared. We will define our surveillance groups based on the number of PSA tests patients receive during the first year following completion of prostatectomy or radiation therapy (Figure) – using an “intention to treat” approach – and analyze patient outcomes from Years 2-10. Operationally, we will compare the outcomes of patients who have 1 vs. 2-3 vs. ≥ 4 PSA tests within the first year. We selected this timeframe as we believe that these patterns would be reflective of the physician’s intended surveillance schedule as opposed to later years which may be more reflective of patient adherence to surveillance recommendations.

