In sensitivity analysis, we will vary this timeframe to define surveillance frequency based on the timing of the first PSA test following completion of prostatectomy or radiation therapy (first PSA within 3 months vs. >3 but within 6 months vs. >6 months); or define comparison groups empirically (most frequent 1/3 of patients vs. middle vs. least frequent 1/3 of patients) – to assess if our findings are robust to these varying exposure groupings [IR-5]. We will also explore using Years 1-2 to define surveillance frequency, and examining patient outcomes from Years 3-10.

Figure 1. Sample Identification and Definition of Timeframes for Measurement

Data Source [IR-1][DR-2][PC-2]: The National Cancer Data Base (NCDB) is a joint program between the Commission on Cancer (CoC) of the American College of Surgeons and the American Cancer Society.⁸ NCDB, started in 1989, is a nationwide cancer outcomes database that includes $>1,400$ CoC-accredited cancer programs and $\sim 70\%$ of all newly diagnosed cancer cases in the US – making its data broadly generalizable and ideal for CER.⁸⁻¹⁰ Systematic, longitudinal follow-up data are updated annually, with multiple data-quality assurance steps taken. **The high quality and representative NCDB data are used for the annual US “cancer statistics” report.**^{11,12} Thus, our results using the NCDB optimizes external validity and generalizability. Data elements are recorded by certified cancer registrars using nationally standardized data item and coding definitions specified by the Facility Oncology Registry Data Standards. Detailed information about data elements collected by the NCDB, standardized data collection protocol, and quality control methods used to assess reported case information is available at: www.facs.org/cancer/ncdb/datasubmission.html.

NCDB Special Study mechanism for primary data collection will be used to obtain the detailed level of information required for this study on data elements which do not currently exist in the NCDB registry – including PSA frequency – and to fill in missing data [MD-1].¹³⁻¹⁵ This will be done using chart abstraction by each of the CoC-accredited centers. For this Aim, the NCDB will randomly select 10 prostate cancer patients diagnosed in 2005-07 from each CoC-

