accredited center, with purposeful sampling in order to achieve approximately the same overall sample size in each of the 6 risk group x treatment cohorts. By randomly selecting a small number of patients from a large number of institutions, we can ensure a broadly representative sample of hospitals and patients, ideal for CER.

Outcomes [RQ-6]: The NCDB annually collects vital status (survival), cancer status (disease free or recurrence), date of recurrence, and treatments for recurrent cancer. This will allow for evaluation of our primary outcome of overall survival, and secondary outcomes of time to recurrence and treatment for recurrent cancer. Additional secondary outcomes will be collected by the special studies mechanism, and include: rates and types of procedures (e.g. biopsy) and tests (e.g. advanced imaging), results of these tests, and treatment for recurrent cancer.

The special studies mechanism will also confirm existing NCDB information regarding cancer status and date of recurrence. Specifically, the PSA dates and results will be abstracted from medical records. Therefore, the investigators are able to define recurrence per standard definitions. These citations provide official definitions for biochemical recurrence after radiation treatment¹⁶ and radical prostatectomy.¹⁷

Cancer registry staff will review hospital and provider records to collect these data, using the same rigorous procedures as primary registry data with specific instructions and training for abstraction by the investigative team and personnel at CoC. These data will be combined with the existing NCDB data to provide the analysis dataset. This Table summarizes the data elements (outcomes) to be collected using the special studies mechanism: (Table 1)

Data Point	Format
Date of imaging	mm/dd/yy
Type of imaging performed	1) bone scan; 2) CT scan; 3) MRI; 4) X-ray; 5) PET scan; 6) other
Date of biopsy/procedure	mm/dd/yy
Biopsy/procedure results	1) benign; 2) malignant; 3) indeterminate
Date of treatment for recurrence	
Type of treatment	1) radiation; 2) surgery; 3) hormone therapy; 4) chemotherapy; 5) other therapy; 6) no treatment

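### Aim 1 takes the PSA count and the procedures and tests from the same chart abstraction, with no visible rule for men followed elsewhere, so shared under-capture could create or inflate the hypothesised association for these secondary outcomes

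*Combined protocol and SAP*

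**What the plan says.** **Exposure.** Under Specific Aim 1, Data Source, the Special Study supplies "data elements which do not currently exist in the NCDB registry – including PSA frequency". The method is stated as "This will be done using chart abstraction by each of the CoC-accredited centers". Under Comparators, "we will compare the outcomes of patients who have 1 vs. 2-3 vs. ≥ 4 PSA tests within the first year".

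**Outcomes.** Under Outcomes: "Additional secondary outcomes will be collected by the special studies mechanism, and include: rates and types of procedures (e.g. biopsy) and tests". The records searched are described as follows: "Cancer registry staff will review hospital and provider records to collect these data". The window is stated under Comparators: the plan will "analyze patient outcomes from Years 2-10".

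**Registry data.** Some outcomes have a second source: "The NCDB annually collects vital status (survival), cancer status (disease free or recurrence), date of recurrence, and treatments for recurrent cancer". Overall survival, the primary outcome, therefore does not depend on the new abstraction.

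**Hypothesis.** "More frequent surveillance increases the receipt of additional procedures and tests in all groups of patients".

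The plan also says that the full variable list is in a separate document, and that a pilot will test whether each element can be collected and may lead to changes.

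**The concern.** An abstractor sees only what the reachable records contain. If a man has some PSA tests at an outside practice, his year-1 count is too low. If he stays with that practice, his later scans and biopsies are also less likely to be found. The two errors occur in the same men and point the same way. Men with incomplete records collect in the 1-test group and bring low recorded procedure rates with them, which is the pattern the hypothesis predicts.

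The visible text does not ask whether a man was still being followed in the abstracted records before his count is read as his schedule, or before an empty procedure field is read as no procedure. The procedures and tests result is the study's main measure of harm from frequent surveillance and is meant to inform patients' decisions. An artefact in it would overstate that harm.

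**Working it through.** The plan gives no figure for this point, so there is none to reproduce. The check asks what the planned comparison would show if PSA frequency had no effect at all.

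**Inputs from the plan**
- Year-1 PSA distribution, Table 2 (SEER-Medicare), low risk: 20% / 61% / 19% for 1 / 2-3 / 4 tests. The top row is read as 4 or more, to match Comparators.
- Cohort size: 14,000 / 6 = 2,333. Alpha 0.05, two-sided.

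**Assumed inputs**
- Share of men followed partly elsewhere: f = 10-30%.
- Chance that each of their tests, and their procedure outcome, is captured: c = 30-75%.
- Split of Table 2 into counts 1 to 5: 0.20 / 0.30 / 0.31 / 0.14 / 0.05.

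**Formula.** Let a_g be the true share of men in group g. Let b_g be the share of incompletely captured men whose captured count falls in g, found by binomial thinning: b_k = Σ p_n × C(n,k) × c^k × (1−c)^(n−k). Recorded risk as a fraction of true risk is

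R_g = [(1−f)a_g + f·c·b_g] / [(1−f)a_g + f·b_g]

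The spurious risk ratio is R_4+ / R_1. The true procedure risk cancels.

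**Worked case, f = 20%, c = 50%**
- b_1 = 0.20×0.5 + 0.30×0.5 + 0.31×0.375 + 0.14×0.25 + 0.05×0.156 = 0.409
- b_4+ = 0.14×0.0625 + 0.05×0.1875 = 0.018
- R_1 = (0.160 + 0.5×0.0818) / (0.160 + 0.0818) = 0.831
- R_4+ = (0.1520 + 0.0018) / (0.1520 + 0.0036) = 0.988
- Spurious risk ratio = 0.988 / 0.831 = 1.19
- Incomplete records in the 1-test group: 0.0818 / 0.2418 = 34%
- Men with no captured PSA: b_0 = 0.224, so 0.20 × 0.224 = 4.5% of the cohort. They fit none of the three groups.

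**Range, low-risk distribution, true risk ratio 1.00**

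| Capture c | f = 10% | f = 20% | f = 30% |
|---|---|---|---|
| 30% | 1.14 | 1.30 | 1.47 |
| 50% | 1.10 | 1.19 | 1.28 |
| 75% | 1.03 | 1.05 | 1.07 |

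With the high-risk distribution (17 / 53 / 30%; 2-3 split equally, top group taken as 4) the values are a little higher: 1.21 at f = 20%, c = 50%, and 1.54 at f = 30%, c = 30%. At f = 20%, c = 50% and an assumed true procedure risk of 30%, recorded risks are 24.5% and 29.8% in groups of about 500 and 569 men. A two-proportion test would then be significant in the hypothesised direction about 48% of the time, against 2.5% with no bias.

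**Contrast.** If PSA tests are still under-captured but the outcome is fully captured elsewhere, the factor c drops out of the numerator, every R_g is 1 and the risk ratio is 1.00. The bias therefore comes from the shared source, not from exposure error alone.

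**Whether the plan's safeguards reach it**
- The alternative exposure groupings under Comparators re-cut the same abstracted PSA data.
- Regression and propensity scores (C3) adjust for measured characteristics. Record completeness is not among those listed under Covariates.
- Imputation (C3, item 5) acts on elements known to be missing. An unseen outside test leaves a count that looks complete.
- Site terms do not address differences in capture between men at one site.
- The unmeasured-factor sensitivity analysis is described for a confounder, not for joint error in exposure and outcome.
- Of the exploratory instruments, provider preference needs surveillance data, and no other Aim 1 source is named. Region helps only if capture does not itself vary by region.

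**What a last-contact rule would do, f = 20%, low-risk distribution**
- *Men who leave the records during year 1* (assumed: departure uniform over the year, tests at random times, all later procedures lost). A man with n tests has captured count 0 to n with equal probability. So b_1 = 0.20/2 + 0.30/3 + 0.31/4 + 0.14/5 + 0.05/6 = 0.314 and b_4+ = 0.14/5 + 0.05×2/6 = 0.045. Then R_1 = 0.160/0.2228 = 0.718, R_4+ = 0.152/0.1609 = 0.944, and the risk ratio is about 1.31. A 12-month contact requirement drops these men, and it returns to 1.0.
- *Men with parallel outside care.* If a share q of them still has a contact in the window, f becomes fq / (1 − f + fq). At q = 1 nothing changes: 1.30 at 30% capture and 1.19 at 50%. At q = 0.9 the values are 1.27 and 1.18.

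**The case against.** The strongest reply is that the size is invented. The documents give neither the share of men followed elsewhere nor the capture rate, and at 75% capture the distortion is only 3-7% under the low-risk distribution. That stands. A reader might infer that the design must manufacture the association in all six cohorts; the documents support only that it could.

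The plan also searches provider as well as hospital records, with training, and the pilot may change the data elements. The variable list is not in view, so a last-contact date may already be collected. These points reduce the concern but do not meet it: the visible text sets no rule for obtaining outside records or for reading an empty field.

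A reader might also infer that survival is biased in the same way. It is not: vital status comes from the registry, so misclassified exposure is the only route. Treatment for recurrence is also collected annually by the registry and does not rest on the charts alone.

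Nor do men who leave wholly all become 1-test men. Those gone from the start have a count of 0 and enter no group, so the bias comes from men with some captured tests.

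Finally, Table 2 should not be read as the basis of the comparators. Those were chosen from published recommendations and stakeholder input; Table 2 is used for power.

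A last-visit rule is also open to criticism. It does little for parallel care, and if its window had no upper limit, eligibility would depend on later visits prompted by recurrence. Both points stand and shape the fix.

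**Conclusion.** The concern holds as a possible bias in secondary outcomes. The shared source is stated in the plan, the direction follows from it, and no visible safeguard reaches it. With no true effect, the spurious risk ratio for 4 or more tests versus 1 is about 1.03-1.47 (low-risk distribution, 10-30% of men affected, 30-75% capture). Those shares and capture rates are assumptions, as is equal capture for tests and procedures.

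It applies to abstracted procedures and tests, and to recurrence and its treatment only so far as these rest on the same charts. It does not show that a positive finding would be an artefact, and it does not overturn the primary survival comparison. A change is worth making because it costs little while the data elements are still open.

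**What to change.** 1. **Data element.** Unless the separate variable list already has it, add before the pilot the date of last documented contact in the abstracted records, and have abstractors mark whether there was a contact in the landmark window below.
2. **Abstracted procedures and tests.** Include men with a documented contact at a 12-month landmark, in a bounded window fixed in advance so that eligibility does not depend on later recurrence visits. End at-risk time at last documented contact.
3. **Other outcomes.** Keep overall survival in the full classified sample, with the documented-follow-up subset as a sensitivity analysis. Keep registry follow-up for registry-collected treatment of recurrence.
4. **Men with no captured PSA.** Report their number by cohort.
5. **Residual bias.** Because the landmark does not remove bias from parallel outside care, add a quantitative bias analysis over stated ranges of f and c. Report residual correlated under-capture as a limit on the procedures and tests conclusion.
6. **Descriptive check only.** Compare the abstracted PSA distribution in men aged 65 and over with Table 2, by risk group. Table 2 is not split by treatment while the sample is balanced on it, so a mismatch would not prove missing records.

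The cost is one date and one marker per man, plus SAP wording. The downsides are fewer men in the procedures and tests comparison, possibly informative censoring at last contact, and results that apply to men followed within the abstracted records. Adding the date after abstraction at more than 1,400 centres would mean going back to the charts.

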The full description of all the variables which will be collected is provided in a separate document. Of note, we will first undergo a pilot study with a limited number of participating sites to test the feasibility of collecting each data element retrospectively. Lessons from the pilot study will inform necessary modifications of data elements collected before embarking on the full with sites across all CoC-accredited centers.

Covariates [IR-3][CI-4]: Data collected at time of diagnosis by the NCDB include, but are not limited to, the following:

- *Demographics:* age, race/ethnicity, marital status, county of residence, census tract data, occupation, tobacco history, rural/urban continuum, insurance

- *Cancer specific variables*: histology/behavior (ICD-0-2, ICD-0-3), diagnostic date. Starting in 2004: PSA level, Gleason score and clinical stage – used to classify patients into low-, intermediate-, and high-risk categories.⁷
- *Comorbidities*: Up to 10 per patient are abstracted and scored per the Charlson-Deyo comorbidity score.¹⁸
- *Hospital characteristics*: unique facility identifier, type of cancer center
- *First course of treatment*: surgery, radiation, hormonal/endocrine, treatment dates.

[figure not shown]
Data Analysis [IR-3]: Patients diagnosed in 2005-2007 will be included. By the time of data analysis, the NCDB will have survival data through 2015, providing 8-10 years of follow-up data for each patient.

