The analysis is stratified by two important factors, risk of recurrence (low, intermediate, high) and type of initial treatment (surgery, radiation); thus, 6 separate analyses will be performed. All outcomes will be defined from years 2-10 from end of prostatectomy or radiation treatment (Figure 1). We will use two modeling strategies to evaluate our outcomes of interest: 1) modified Poisson/binary regression^{19,20} with sandwich standard errors to estimate risks of the events of interest during a set follow-up period; and 2) Cox Proportional Hazards regression [CI-3]. Using the modified Poisson/binary regression models, we will estimate the risk of experiencing the outcome of interest (death, recurrence, use of procedures and tests, treatment for recurrence) during a defined interval beginning in the second year following treatment. Additionally, we will estimate overall survival using adjusted Cox Proportional Hazards regression models. We will evaluate the proportional hazards assumption by generating Kaplan-Meier survival curves and through testing interactions between relevant covariates and time in the Cox model. Covariates that violate the proportional hazards assumption will be used as stratification variables as appropriate. In sensitivity analyses, we will generate a propensity score (where the patient, provider and hospital characteristics measured at the time of prostatectomy or radiation completion are included in the propensity score) and create a matched cohort of patients to evaluate using Kaplan-Meier survival models [described in detail in C3]. For secondary outcomes, time to recurrence will be modeled for each surveillance frequency using a competing risk analysis as described by Fine and Gray.²¹ Similar methods will be used to calculate the cumulative incidence of procedures and tests and treatment for recurrence.

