Power calculations used a range of 10-year overall survival rates from 70-80%, $\alpha=.05$, and two-sided test. Using distributions in Table 2, there is >80% power to detect a 5% survival difference among groups of different surveillance frequencies. Our stakeholders have indicated this level of survival difference to be meaningful.

Potential problems and alternative strategies:

Although the analysis will stratify by prostate cancer risk status, it is possible that within each

risk strata, patients with clinical and pathological features that are associated with a worse prognosis may be followed more frequently than patients with a better prognosis. One way we have proposed to address this issue is with instrumental variable analysis (Page 11). We will test two commonly-used, potential instrumental variables: region and the provider's most commonly used surveillance regimen (commonly called “provider preference”). Another way to address this in our primary analysis is to account for risk variables (clinical and pathological features) within each risk strata. We will plan to incorporate this in the primary analysis as control variables within the outcome models or within the propensity score model, as appropriate to the research question.

Our definition of comparison groups is based on published recommendations and stakeholder guidance. However, schedules for surveillance PSA tests in this observational cohort may not precisely match the anticipated 3, 6, and 12 month intervals. Multiple classification schemes will be assessed for characterizing the surveillance intervals, as described on page 2. The analysis will be repeated using alternative classification schemes, and sensitivity analyses will be used to determine if there are meaningful differences in the results based on classification of surveillance intervals, and to optimize our classification of surveillance frequency [IR-5].

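### Aim 1 outcomes run to Year 10 after treatment, which at most about a third of men can complete for survival, and the binary-risk models show neither a shorter horizon nor a way to handle shorter follow-up

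*Combined protocol and SAP*

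**What the plan says.** The Aim 1 Comparators and Data Analysis sections both set the outcome window at Years 2-10. The latter fixes the time origin: "All outcomes will be defined from years 2-10 from end of prostatectomy or radiation treatment". That sentence points to Figure 1, captioned "Figure 1. Sample Identification and Definition of Timeframes for Measurement", which is not reproduced in the text available for this review.

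On available follow-up, Data Analysis says that for men diagnosed in 2005-2007 "the NCDB will have survival data through 2015, providing 8-10 years of follow-up data for each patient".

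Two modelling strategies follow. Modified Poisson/binary regression is used "to estimate risks of the events of interest during a set follow-up period", covering death, recurrence, procedures and tests, and treatment for recurrence, "during a defined interval beginning in the second year following treatment". Cox regression is used for overall survival. Section C3 names both as the primary approach. Separately, recurrence gets a Fine-Gray analysis, and "Similar methods will be used to calculate the cumulative incidence of procedures and tests and treatment for recurrence".

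**The concern.** A binary-risk model without weights needs each man's event status known at the same end point. The only end point in the visible text is Year 10 after treatment, and the plan's own follow-up figure says many men will have 8 or 9 years. The 8-10 years also matches counting from diagnosis, whereas the outcome clock starts later, at end of treatment. No visible rule says how a man alive and event-free at 8.5 years enters the model.

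What is at stake is mainly the absolute risks. The stated rationale for Aim 1 is that "successful completion of the proposed research will contribute novel, currently unavailable, data to inform patient decision-making", so percentages may well be quoted to patients. Two analysts following the text could report quite different ones.

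**Working it through.** **Inputs from the plan.** Diagnosis 2005-2007; survival data through 2015, read as 31 December 2015; window from the start of Year 2 to the end of Year 10 after treatment (1 to 10 years); 10-year survival 70-80%, from Statistical power ("Power calculations used a range of 10-year overall survival rates from 70-80" percent).

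**Assumptions, not in the documents.** Even accrual over the three years; constant hazard; no loss before the cutoff; lag *g* from diagnosis to end of treatment of 0, 3 or 6 months, with 9 months as a further case.

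**Step 1: reproduce the stated follow-up.** 2015 − 2007 = 8 and 2015 − 2005 = 10, which gives the stated 8-10 years, counted from diagnosis.

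**Step 2: who can complete Year 10.** With *u* the years from 1 January 2005 to diagnosis (uniform on 0-3), follow-up from end of treatment is F = 11 − u − g. F ≥ 10 requires u ≤ 1 − g, so the share is (1 − g)/3. Only men diagnosed in 2005 can qualify.

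**Step 3: true risk.** λ = −ln(S10)/10. Years 2-10 risk among men alive at 1 year = 1 − exp(−9λ): 27.5%, 22.8% and 18.2% for S10 = 70%, 75% and 80%.

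**Step 4: survivors with short follow-up scored event-free.** Scored risk = mean over u of 1 − exp(−λ(min(F,10) − 1)).

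| Lag (months) | Can complete Year 10 | Scored, S10 70% | Scored, S10 75% | Scored, S10 80% | Shortfall (points) |
|---|---|---|---|---|---|
| 0 | 33% | 25.7% | 21.3% | 17.0% | 1.2-1.8 |
| 3 | 25% | 25.2% | 20.9% | 16.6% | 1.6-2.2 |
| 6 | 17% | 24.7% | 20.4% | 16.3% | 1.9-2.8 |
| 9 | 8% | 24.1% | 19.9% | 15.9% | 2.4-3.4 |

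Reading 8-10 years instead as exactly 8, 9 and 10 years in equal thirds gives 20.5% against 22.8% at 75% survival, 2.3 points short.

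**Step 5: the same survivors dropped instead.** Events observed before the cutoff stay in, but event-free men with short follow-up leave. Estimated risk = scored / (scored + share completing × true survival over the window). At S10 = 70% and 6 months: 0.2468 / (0.2468 + 0.1667 × 0.7254) = 67%. At S10 = 80% and no lag: 0.1696 / (0.1696 + 0.3333 × 0.8181) = 38%. So the result is 38-67% against a true 18-27%. Restricting by diagnosis date, regardless of event status, avoids this bias but keeps only about 778, 583 or 389 of 2,333 men per cohort at 0, 3 or 6 months.

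**Step 6: the group comparison under event-free scoring.** For 80% against 75% survival with equal follow-up in both groups, the true risk ratio is 0.798 and the scored ratio 0.795-0.796. The true risk difference is 4.6 points; scored, it is 4.3, 4.3, 4.2 and 4.1 at lags of 0, 3, 6 and 9 months, so it shrinks by about 0.3 to 0.5 points.

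**The case against.** The strongest reply is that the plan does not say it will do any of this. It describes the binary-model period as set and defined, which is fixed-horizon language. Years 2-10 may be only the outer window, with a shorter interval placed inside it, possibly in Figure 1. A reader might infer that event-free scoring is planned; no section says so, and the commitment in C3 (Handling of missing data) to examine missingness and account for all patients points, if anything, the other way. That section does not, however, mention follow-up cut short by the data cutoff. This objection stands against any claim of demonstrated bias. It does not supply an end point or a rule in the visible text.

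A reader might also infer that the primary survival comparison is compromised. It is not: Cox handles this censoring for overall survival, and the Fine-Gray-type analyses do so for recurrence, procedures and tests, and treatment, so every outcome listed for the binary models has a sound parallel analysis. That stands, and it limits severity, but it does not say how the other primary model is to be run.

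Nor should a shortfall of about 2 points in the level of risk be set directly against the 5% survival difference that stakeholders called meaningful. That figure is a difference between groups, and the comparable effect is the 0.3-0.5 point shrinkage.

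Finally, the 2015 limit is stated for survival data only. No end date is visible for chart-abstracted outcomes, so the size of any shortfall there is not established.

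**Conclusion.** The point holds as a conditional one. The only visible outcome window cannot be completed for survival by most men: 67% cannot with no lag and 83% cannot at an assumed 6 months. The binary models show no other horizon and no handling of shorter follow-up. If they are fitted over Years 2-10 without adjustment, absolute death risk is understated by about 1.2-2.8 points under event-free scoring, or greatly overstated if those survivors are dropped.

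These sizes rest on an end-2015 cutoff, even accrual, constant hazard, a 0-6 month lag and 70-80% 10-year survival. The near-constant risk ratio also requires follow-up to be balanced across surveillance groups. If Figure 1 fixes a shorter, completable interval, what remains is to say so in the text and to correct the follow-up statement. Severity: minor to moderate.

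**What to change.** Unless Figure 1 already does so, choose one of the following and state it in Aim 1 Data Analysis:

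- **A completable horizon.** Fit the binary models over a window every man can complete from end of treatment, for example Years 2-7, which all can reach if the lag is 12 months or less (11 − 3 − 1 = 7). Cost: a different estimand with fewer events. At 75% 10-year survival the risk is 1 − exp(−6λ) = 15.9% rather than 22.8%, and the 80% against 75% contrast is 3.3 rather than 4.6 points.
- **The Years 2-10 horizon with censoring handled.** Use inverse-probability-of-censoring-weighted or pseudo-observation regression, which can also handle men lost before the cutoff. Cost: for a group of 420 men (18% of 2,333) at 75% survival, the approximate (Greenwood) standard error is 2.2-2.4 points at 0-6 months' lag (2.6 at 9 months), against 2.0 with complete follow-up and 1.8 for Years 2-7. It also relies on risk not changing by diagnosis year, since only men diagnosed in 2005 reach Year 10.

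In either case, state how survivors with incomplete follow-up enter the binary models, and restate the 8-10 years as time from end of treatment. This needs SAP wording and minor programming, and no new data.
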